13.4.3. Event of Special Interest

None

Clinical Study Protocol

Johnson & Johnson Vision Care, Inc.

13.5. Reporting of Pregnancy

Subjects reporting pregnancy (by self-report) during the study will be discontinued after the event is recorded as an Adverse Event. Once discontinued, pregnant participants and their fetuses will not be monitored for study related purposes. At the Investigator's discretion, the study participant may be followed by the Investigator through delivery. However, this data will not be collected as part of the clinical study database. Pregnant participants are not discontinued from contact lens or solution related studies for safety concerns, but due to general concerns relating to pregnancy and contact lens use. Specifically, pregnant women are discontinued due to fluctuations in refractive error and/or visual acuity that occur secondary to systemic hormonal changes, and not due to unforeseen health risks to the mother or fetus.

14. STATISTICAL METHODS

14.1. General Considerations

All data summaries and statistical analyses will be performed using the SAS software version 9.4 (SAS Institute, Cary, NC). Throughout the analysis of data, the results for each subject/eye will be used when available for summarization and statistical analysis. Unscheduled visits will be summarized separately and will be excluded from the statistical analysis.

Summary tables (Descriptive statistics and/or frequency tables) will be provided by lens type for all baseline variables, efficacy variables and safety variables as appropriate. Continuous variables will be summarized with descriptive statistics (n, mean, standard deviation [SD], median, minimum and maximum). Frequency count and percentage of subjects or eyes within each category will be provided for categorical data.

14.2. Sample Size Justification

The study was powered to demonstrate non-inferiority of the Test lens relative to the Control with respect to binocular visual performance with minimum of 90% power and two-sided type I error of 5%. Assuming no difference between Test and Control, the required sample size to achieve non-inferiority for distance, intermediate and near visual performance at different lighting conditions are summarized in Table 5. The intra-class correlation (ICC) and standard deviations (STD) used in the sample size calculations were from a similar study (CR6267). The sample size calculations were conducted using the SAS procedure PROC POWER for paired t-test.

Table 5: Required sample to achieve non-inferiority

Distance	Lighting Condition	STD Test	STD Control	ICC	Sample Size
Distance	High Luminance High Contrast	0.091	0.094	0.60	31
	High Luminance Low Contrast	0.091	0.105	0.68	29
	Low Luminance High Contrast with Distance Goggles	0.101	0.092	0.64	31

Clinical Study Protocol

Johnson & Johnson Vision Care, Inc.

Intermediate	High Luminance High Contrast	0.095	0.116	0.68	34
	High Luminance Low Contrast	0.107	0.129	0.71	38
	Low Luminance High Contrast with Near Goggles	0.125	0.152	0.81	36
Near	High Luminance High Contrast	0.086	0.113	0.63	36
	High Luminance Low Contrast	0.103	0.130	0.69	40
	Low Luminance High Contrast with Near Goggles	0.115	0.137	0.73	40

STD: standard deviation, ICC: intra-class correlation

After adjusting for 7% drop-outs or lost to follow-up, the plan is to enroll 48 subjects with a target completion of 40 subjects.

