2.3. Hypotheses

Primary Hypotheses:

The Test lens will be non-inferior to the Control lens with respect to binocular contact lens-corrected visual performance at near, intermediate and distance under high luminance high contrast, Dim luminance high contrast and high luminance low contrast conditions. A non-inferiority margin of 0.05 on logMAR scale will be used.

Secondary Hypotheses:

No secondary hypotheses will be tested. All secondary endpoints will be evaluated with summary tables (see Section 14 for more details). The following will be calculated:

- Average (SD) comfort scores on CLUE scale by study lens at each follow-up visit
- Proportion of eyes with clinically significant (Grade 3 or 4) slit lamp findings.
- Proportion of eyes with reported ocular symptoms.

Clinical Study Protocol

Johnson & Johnson Vision Care, Inc.

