5.2. Masking

This is a single-masked (partial) study with the subjects being masked. Subjects will be aware that there are differences in modalities between lens types however they will not be told anything regarding the optical design other than the design is intended to correct for their spherical refractive error and presbyopia. Subjects will be unaware of the identity of the assigned investigational products. Investigators and clinical site personnel involved in the data collection will be aware of the identity of the assigned investigational products.

Clinical Study Protocol

Johnson & Johnson Vision Care, Inc.

The identity of the study lenses will be masked to subjects by over labeling the blister packs with a label containing the study number, lot number, sphere power, add power, expiration date and the randomization codes. Investigators and medical monitor will have access to the decode information translating the randomization codes into Test and Control arms.

Under normal circumstances the mask should not be broken until all subjects have completed the study and the database is finalized. Otherwise, the mask should be broken only if specific emergency treatment/course of action would be dictated by knowing the treatment status of the subject. In such cases, the Investigator may, in an emergency, contact the medical monitor. In the event the mask is broken, the Sponsor must be informed as soon as possible. The date, time, and reason for the unmasking must be documented in the subject record. The Investigator is also advised not to reveal the study treatment assignment to the clinical site or Sponsor personnel.

Subjects who have had their treatment assignment unmasked are expected to return for all remaining scheduled evaluations. Subjects who are discontinued may be replaced.

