14.3. Analysis Populations

The following analysis populations will be defined and used in the analysis and presentation of the data.

All Enrolled:

All Enrolled Population includes all subjects with recorded data in the electronic Case Report Form (eCRF) database

Intent-To-Treat (ITT):

Intent-to-treat will include all the subjects who were randomized to study treatment. Subjects will be analyzed as per randomized treatment. At least one observation should be recorded. Discontinued subjects, subjects with major protocol deviations and ineligible subjects who were inadvertently randomized will be included in the ITT analyses.

Safety Population:

All subjects who were administered any test article excluding subjects who drop out prior to administering any test article. At least one observation for safety endpoints should be recorded (e.g. ocular symptom, slit-lamp finding, etc.) or on after treatment start date. Subjects will be analyzed as per treatment received.

Per Protocol (PP)

All subjects who have successfully completed the study and did not substantially deviate from the protocol as determined by the trial cohort review committee prior to database hard lock. Justification of excluding subjects with protocol deviations from the per-protocol population set will be documented in a memo to file.

The primary analysis will be conducted on the per-protocol population. A sensitivity analysis will be conducted on the ITT population.

Clinical Study Protocol

Johnson & Johnson Vision Care, Inc.

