14.4. Level of Statistical Significance

All planned analysis for this study will be conducted with an overall type I error rate of 5%.

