14.5. Primary Analysis

Visual Performance:

Binocular visual performance at 2-week follow-up visit will be analyzed separately by lighting condition and distance using a Bayesian repeated measurement random-effects model to compare between Test and Control lenses. Each regression model will include baseline values, lens type, lens wearing sequence and lens wearing period as fixed effects and investigational site as random effect. Other subject characteristics such as age, gender will be included as fixed effects when appropriate. Unstructured covariance matrix will be used to model the residual errors among observations within subjects. Non informative prior distributions will be used for the coefficients in the models as well as for the error terms. Independent vague normal $N(0,1000)$ priors will be used for the regression coefficients, inverse gamma $IG(0.001, 0.001)$ for the variance of the random effect site and inverse Wishart for the residual errors. A Markov-Chain Monte Carlo (MCMC) sampling algorithm will be used to carry out the marginal posterior distributions of the parameters. Results will be reported as regression coefficient mean estimates with 95% credible intervals.

The null and alternative hypotheses for non-inferiority of Test lens relative to Control are as follows:

$$H_0: \Delta > 0.05$$
$$H_A: \Delta \leq 0.05$$

where Δ is the posterior mean difference in visual performance between Test and Control (Test minus Control). Non-inferiority will be declared if the upper bound of the credible interval of the posterior mean difference is less than 0.05.

The primary analysis will be conducted on the per-protocol population. A sensitivity analysis will be conducted on the ITT population.

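### The 90% power in Section 14.2 holds for each of nine comparisons alone; joint power for the all-nine hypothesis in Section 2.3 is lower and not stated, and Section 14.5 does not say all nine must pass

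*Combined protocol and SAP*

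**What the plan says.** Section 2.3 gives the primary hypothesis in one sentence: the Test lens is to be non-inferior "at near, intermediate and distance under high luminance high contrast, Dim luminance high contrast and high luminance low contrast conditions", with a margin of 0.05 logMAR. Three distances by three conditions make nine comparisons.

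Section 14.2 states that the study was powered for non-inferiority "with respect to binocular visual performance with minimum of 90% power and two-sided type I error of 5"%. Table 5 then lists one paired t-test sample size for each distance and lighting combination, the largest being 40. The section closes: "After adjusting for 7% drop-outs or lost to follow-up, the plan is to enroll 48 subjects with a target completion of 40 subjects".

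Section 14.5 says: "Binocular visual performance at 2-week follow-up visit will be analyzed separately by lighting condition and distance". Its decision rule refers to a single interval: "Non-inferiority will be declared if the upper bound of the credible interval of the posterior mean difference is less than 0.05". It does not say how many of the nine intervals must meet the rule.

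Section 14.4 adds: "All planned analysis for this study will be conducted with an overall type I error rate of 5"%. No multiplicity method is named.

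**The concern.** Table 5 answers the question of how many subjects each comparison needs by itself. The hypothesis in Section 2.3 asks for more, since its distances and conditions are joined by 'and'. If all nine must pass, the unadjusted intervals control type I error, a mixed result means the hypothesis is not met, and joint power is the figure that matters. The plan does not give it. A reader of Section 14.2 could take 90% as the chance of meeting the primary hypothesis when the lenses are truly equal.

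If the nine were meant as separate claims, the 90% would be the right kind of power. But nine unadjusted 95% intervals would then not assure the overall error rate in Section 14.4. On either reading, one stated property of the design is not delivered or not assured.

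The practical risk is a mixed result, say eight comparisons passing and one near comparison failing, with no written rule on whether the primary hypothesis was met. Section 5.2 says "Investigators and clinical site personnel involved in the data collection will be aware of the identity of the assigned investigational products", so the rule should be in writing before results can influence it.

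**Working it through.** **Inputs.** From Table 5: Test SD, Control SD and ICC for each comparison. From Section 2.3: margin 0.05. From Section 14.2: true difference 0, paired t-test, two-sided 5%, target of 40 completers.

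**Step 1: reproduce Table 5.** The SD of the paired difference is √(s₁² + s₂² − 2·ICC·s₁·s₂). For near, high luminance low contrast: √(0.103² + 0.130² − 2 × 0.69 × 0.103 × 0.130) = √(0.010609 + 0.016900 − 0.018478) = 0.0950. Power at n comes from the noncentral t distribution with n − 1 degrees of freedom and noncentrality 0.05√n / SD, tested at one-sided 0.025. For this row at n = 40 the noncentrality is 0.05 × 6.325 / 0.0950 = 3.33, and the power is 0.9005.

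| Comparison | SD of difference | Table 5 n | Recomputed n | Power at 40 | Power at 44 | Power at 48 |
|---|---|---|---|---|---|---|
| Distance, bright high contrast | 0.0828 | 31 | 31 | 0.961 | 0.975 | 0.984 |
| Distance, bright low contrast | 0.0794 | 29 | 29 | 0.973 | 0.983 | 0.990 |
| Distance, dim high contrast | 0.0823 | 31 | 31 | 0.963 | 0.976 | 0.985 |
| Intermediate, bright high contrast | 0.0866 | 34 | 34 | 0.945 | 0.963 | 0.975 |
| Intermediate, bright low contrast | 0.0921 | 38 | 38 | 0.917 | 0.940 | 0.957 |
| Intermediate, dim high contrast | 0.0892 | 36 | 36 | 0.933 | 0.953 | 0.967 |
| Near, bright high contrast | 0.0890 | 36 | 36 | 0.934 | 0.954 | 0.968 |
| Near, bright low contrast | 0.0950 | 40 | 40 | 0.901 | 0.927 | 0.946 |
| Near, dim high contrast | 0.0948 | 40 | 40 | 0.902 | 0.928 | 0.947 |

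All nine rows match. One-sided 0.05 would give 24 to 33, so the two-sided 5% in Section 14.2 means 2.5% on the non-inferiority side.

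**Step 2: bounds on joint power at 40 completers, whatever the correlations.** It cannot exceed the smallest row power, 0.9005. It cannot fall below 1 − Σ(1 − power) = 0.43. Under independence it is the product of the nine row powers, 0.55.

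**Step 3: joint power with correlated differences.** The documents give no correlations among the nine paired differences, so these are assumed. Nine correlated paired t-tests were simulated (40,000 trials per case, Monte Carlo standard error at most 0.0025). Because 48 × 0.93 = 44.6, about 44 completers would follow from the stated 7% dropout.

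| Correlation | 40 completers | 44 | 48 |
|---|---|---|---|
| 0 | 0.55 | 0.66 | 0.75 |
| 0.5 | 0.71 | 0.77 | 0.83 |
| 0.7 | 0.77 | 0.82 | 0.87 |
| 0.9 | 0.84 | 0.88 | 0.91 |
| 0.95 | 0.87 | 0.90 | 0.93 |
| 0.8 within a viewing distance, 0.5 between | 0.75 | 0.81 | 0.86 |

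The number of completers needed for 90% joint power is about 59, 56, 52 and 47 at equal correlations of 0, 0.5, 0.7 and 0.9.

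**Step 4: the separate-claims reading.** Here the question is the chance of at least one false claim at 40 completers, against 2.5% per test. With all nine true differences at the margin it is 0.20, 0.14, 0.10, 0.06 and 0.05 at correlations 0, 0.5, 0.7, 0.9 and 0.95 (check at zero correlation: 1 − 0.975⁹ = 0.204). With only the near low-contrast and near dim differences at the margin and the others zero, it is 0.049, 0.046, 0.042, 0.034 and 0.033 (check: 1 − 0.975² = 0.049).

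**The case against.** The strongest reply is that Section 14.2 already shows the basis of its 90%. Table 5 follows directly, has one row per comparison, and the target is its largest entry. The 90% can be read as the minimum over rows, and on that reading it is correct. The heading in Section 2.3 is plural and Section 14.5 analyses the comparisons separately, so nine separate claims may have been intended. The size of any shortfall rests on unknown correlations. The same subjects supply all nine measurements, so zero correlation is an extreme bound, and more than 40 may complete. Section 2.1 calls the study a pilot.

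Much of this stands. No figure in Table 5 is wrong, and the true shortfall could be small. Measured against 5% rather than 2.5%, the two-at-the-margin error rates do not exceed the stated level; only the extreme nine-at-the-margin case does.

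Three things remain. The ceiling of 0.9005 at 40 completers needs no correlation assumption, and 40 is the number the plan itself targets. The primary analysis is on the per-protocol set, "as determined by the trial cohort review committee prior to database hard lock", which may be smaller than the number of completers. And the separate-claims reading does not rescue the plan: it makes the 90% apt but leaves the overall error rate in Section 14.4 without a method behind it. Pilot status limits the consequences, but the protocol still states a margin, a power and a decision rule, and these should agree.

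**Conclusion.** The concern holds. The 90% is correct for each comparison alone but is not the power for the hypothesis as Section 2.3 most naturally reads. For moderate correlations of 0.5 to 0.7, truly equal lenses would fail to meet all nine about 23% to 29% of the time at 40 completers (1 − 0.77 and 1 − 0.71), against the 10% or less that Section 14.2 suggests.

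The figures assume a true difference of zero, the Table 5 SDs and ICCs, and the paired t-test the plan used for sizing. The Bayesian covariate model in Section 14.5 could shift them in either direction. This is a point of wording and disclosure that should be fixed; it does not call the estimates or the conduct of the study into question.

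**What to change.** In Section 14.5, add a sentence consistent with Section 2.3, as early as possible and in any case before database hard lock: *The primary hypothesis is met only if the upper 95% credible bound is below 0.05 for all nine comparisons; no alpha adjustment is needed.* Only if partial claims are intended, pre-specify a fixed sequence or another multiplicity procedure instead.

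In Section 14.2, describe the power as *at least 90% for each comparison taken alone*. Report the joint power for all nine beside it, with the correlations assumed, preferably estimated from the earlier study that supplied the SDs and ICCs.

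The cost is one sentence, one wording change and one recalculation from the earlier study's data. No subjects are added. The downside is a less favourable stated power for the primary hypothesis.

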14.3. Analysis Populations

The following analysis populations will be defined and used in the analysis and presentation of the data.

All Enrolled:

All Enrolled Population includes all subjects with recorded data in the electronic Case Report Form (eCRF) database

Intent-To-Treat (ITT):

Intent-to-treat will include all the subjects who were randomized to study treatment. Subjects will be analyzed as per randomized treatment. At least one observation should be recorded. Discontinued subjects, subjects with major protocol deviations and ineligible subjects who were inadvertently randomized will be included in the ITT analyses.

Safety Population:

All subjects who were administered any test article excluding subjects who drop out prior to administering any test article. At least one observation for safety endpoints should be recorded (e.g. ocular symptom, slit-lamp finding, etc.) or on after treatment start date. Subjects will be analyzed as per treatment received.

Per Protocol (PP)

All subjects who have successfully completed the study and did not substantially deviate from the protocol as determined by the trial cohort review committee prior to database hard lock. Justification of excluding subjects with protocol deviations from the per-protocol population set will be documented in a memo to file.

The primary analysis will be conducted on the per-protocol population. A sensitivity analysis will be conducted on the ITT population.

Clinical Study Protocol

Johnson & Johnson Vision Care, Inc.

14.4. Level of Statistical Significance

All planned analysis for this study will be conducted with an overall type I error rate of 5%.

14.5. Primary Analysis

Visual Performance:

Binocular visual performance at 2-week follow-up visit will be analyzed separately by lighting condition and distance using a Bayesian repeated measurement random-effects model to compare between Test and Control lenses. Each regression model will include baseline values, lens type, lens wearing sequence and lens wearing period as fixed effects and investigational site as random effect. Other subject characteristics such as age, gender will be included as fixed effects when appropriate. Unstructured covariance matrix will be used to model the residual errors among observations within subjects. Non informative prior distributions will be used for the coefficients in the models as well as for the error terms. Independent vague normal $N(0,1000)$ priors will be used for the regression coefficients, inverse gamma $IG(0.001, 0.001)$ for the variance of the random effect site and inverse Wishart for the residual errors. A Markov-Chain Monte Carlo (MCMC) sampling algorithm will be used to carry out the marginal posterior distributions of the parameters. Results will be reported as regression coefficient mean estimates with 95% credible intervals.

The null and alternative hypotheses for non-inferiority of Test lens relative to Control are as follows:

$$H_0: \Delta > 0.05$$
$$H_A: \Delta \leq 0.05$$

where Δ is the posterior mean difference in visual performance between Test and Control (Test minus Control). Non-inferiority will be declared if the upper bound of the credible interval of the posterior mean difference is less than 0.05.

The primary analysis will be conducted on the per-protocol population. A sensitivity analysis will be conducted on the ITT population.

